2.4 Randomization and blinding

Not applicable, as this is a single-sequence, open-label study.

2.5 Sample Size

No confirmatory statistical tests are planned in the study.

Approximately 20 subjects will be enrolled to have at least 18 subjects in the i.v. Safety Set. In the GRIPHON Phase 3 pivotal study of selexipag, a proportion of 7.5% of subjects prematurely discontinued the study (i.e., without a morbidity/mortality event) due to prostacyclin-associated adverse events (AEs) across the titration and maintenance phases. It is expected that the proportion of early discontinuations during the entire study will not be higher than 10% (i.e., that approximately 18 subjects will enter the i.v. period).

A sample size of 18 subjects in the i.v. Safety Analysis Set will ensure that, if the true rate of discontinuations due to prostacyclin-associated AEs is between 5% and 10%, the half-width of the 95% confidence interval (CI) will be below 35%.

The precision achieved with a sample size of approximately 18 subjects in the i.v. Safety Set is considered adequate for this study (e.g., the upper boundary of the CI for the i.v. Safety Analysis Set excludes values above 35%, and for the Safety Analysis Set, above 32%).

3 OBJECTIVES

3.1 Primary objective

The primary objective of this study is to assess whether temporary switching from a stable oral dose of selexipag to an i.v. dose of selexipag providing comparable exposure (e.g., area under the plasma concentration-time curve during a dose interval at steady state [$AUC_{t, ss}$], maximum plasma concentration at steady state [$C_{max, ss}$]) to active metabolite ACT-333679 and switching back to the initial oral dose of selexipag is safe and well tolerated in subjects with stable PAH.

3.2 Other objectives

Other objectives of the study are:

- To evaluate the safety and tolerability of selexipag during each study period.
- To evaluate the PK of selexipag and its active metabolite, ACT-333679, at a stable oral dose at steady state and after the switch from selexipag oral to selexipag i.v. in subjects with stable PAH.

4 ANALYSIS SETS

4.1 Definitions of analysis sets

The following analysis sets were introduced in Section 10.1 of the protocol:

4.1.1 Screened Analysis Set

The **Screened Analysis Set** (SCR) includes all subjects who were screened and received a subject identification number.

4.1.2 Full Analysis Set

Not applicable in this study.

4.1.3 Safety Analysis Set

The Safety Analysis Set (SAF) includes all enrolled (included in the study on Day 1) subjects who received at least one dose of Uptravi or i.v. selexipag during any of Period 1, Period 2, or Period 3 of the study.

4.1.4 i.v. Safety Analysis Set

The i.v. Safety Analysis Set (ivSAF) includes all subjects who received at least one dose of i.v. selexipag.

4.1.5 Pharmacokinetic Analysis Set

The Pharmacokinetic Analysis Set (PKS) comprises all subjects included in the SAF who received an Uptravi dose on Day 1 and the three doses of i.v. selexipag, and who complied with the protocol in a way that the PK measurements of the study are not affected. Protocol deviations resulting in an exclusion from the PKS are shown in [Table 3](#).

Additional rules for exclusion from the PKS may be defined prior to database lock and reflected in this document.

Table 3 Protocol deviations leading to an exclusion from the PKS

Category	Protocol deviation code(s)	Identifier	Level of exclusion
Protocol deviation during screening period	206	Dose of Uptravi not stable for at least 28 days before Visit 2 (INCL 6)	Subject
	209	Subject with known and documented moderate and severe hepatic impairment (EXCL 2)	Subject
	210	Subject received gemfibrozil at any time since initiation of Uptravi (EXCL 3)	Subject
	214	Subject with renal failure and ongoing or planned dialysis (EXCL 7)	Subject
	217	Subject with another investigational treatment within 3 months of Visit 1 (EXCL 10)	Subject
Protocol deviation during treatment and observation period	305	Pre-dose PK blood sample collected after the morning dose on Day 1 or Day 3	Data point*
	306	Any post-AM dose PK sample collected after administration of the following PM dose on Day 1 or Day 3	Data point*
	316	Uptravi was not interrupted during i.v. selexipag treatment	Subject
	312	25 min or 87 min post-infusion start PK blood sample on Day 3 collected from the same arm as the infusion line	Data point*
	313	Subject did not discontinue i.v. selexipag treatment despite missing one infusion	Subject
	318	Dose of PAH medications (including diuretics) not stable between Visit 1 (screening) and last PK blood sample collection on Day 3	Subject
	321	Uptravi not administered or Uptravi dose missing on Day 1	Subject
	322	Uptravi dose on Day 1 is different from stable dose at Visit 1 (screening)	Subject
	323	Any i.v selexipag dose is not corresponding to subject's stable dose of Uptravi (i.e., ≥ 225 ug)	Subject

* If 2 or more data points are excluded from a 12-hour PK profile (i.e., on Day 1 or Day 3), the subjects must be excluded from the PKS. i.v. = intravenous; PK = pharmacokinetic; PKS = Pharmacokinetic Analysis Set.

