5.1.4 Study treatment administration

The following infusion scheme is to be followed:

- Start with an infusion rate of 20 mL/h (0.333 mL/min) for 15 min for the first 5 mL.
- Increase infusion rate to 37.5 mL/h (0.625 mL/min) for 72 min for infusion of the remaining 45 mL.

Note: A dedicated infusion line must be used for i.v. selexipag administration. No other drugs or solutions should be administered through this line.

The following information will be collected in the CRF to document each i.v. selexipag administration:

- Date of administration.
- Concentration of the i.v. infusion solution.
- For each infusion rate: clock time of start and end.

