7.2.5.1.1 Timing for sampling

For all subjects, a total of 14 blood samples will be drawn.

PK blood samples will be collected as displayed in [Table 3](#).

On Day 1, plasma concentrations of selexipag and ACT-333679 will be measured at pre-dose (trough) and 1, 2, 4, 6, 8, and 12 hours after the morning dose of Uptravi.

On Day 3, plasma concentrations of selexipag and ACT-333679 will be measured at pre-dose (trough) and 25 min, 87 min (i.e., immediately before stopping the infusion), 4, 6, 8, and 12 hours after initiation of the morning i.v. infusion of selexipag.

The allowed time window is \pm 5% from the scheduled time point (refer to laboratory manual for conversion table between % and minutes).

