7.8.3 Pharmacokinetic variables

Plasma PK parameters of selexipag and its active metabolite, ACT-333679, will be derived by non-compartmental analysis of the concentration-time profiles.

The PK parameters will be calculated on the basis of the real blood sampling time points (in relation to the last selexipag intake during each period).

The measured individual plasma concentrations of selexipag will be used to directly obtain $C_{trough, ss}$, $C_{max, ss}$, and $t_{max, ss}$.

$AUC_{\tau, ss}$ will be calculated according to the linear trapezoidal rule using the measured concentration-time values above the limit of quantification (LOQ) during one dosing interval at steady state.

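### A Day 3 profile that loses only its 87 min (end-of-infusion) sample stays in the PKS, so parent selexipag i.v. Cmax,ss and AUCτ,ss are understated; ACT-333679 is largely spared

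*SAP*

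**What the plan says.** SAP 4.1.5, Table 3, code 312 covers this deviation: "25 min or 87 min post-infusion start PK blood sample on Day 3 collected from the same arm as the infusion line". Its level of exclusion is the data point, not the subject. The footnote turns data-point exclusions into exclusion of the subject only under the condition "If 2 or more data points are excluded from a 12-hour PK profile", counted separately for Day 1 and Day 3.

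Protocol 7.2.5.1.1 schedules the Day 3 samples at pre-dose and "25 min, 87 min (i.e., immediately before stopping the infusion), 4, 6, 8, and 12 hours", seven in all.

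SAP 7.8.3 derives Cmax,ss, tmax,ss and Ctrough,ss without interpolation: "The measured individual plasma concentrations of selexipag will be used to directly obtain" these parameters. AUCτ,ss "will be calculated according to the linear trapezoidal rule using the measured concentration-time values above" the limit of quantification.

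Two other provisions come close. SAP 7.8.4.3 leaves out parameter values derived from concentrations that the PK expert judged implausible. SAP 4.1.5 allows further PKS exclusion rules before database lock. Neither is tied to code 312, and Table 3 has no entry for an 87 min sample that was never drawn.

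**The concern.** The footnote counts samples as if they were interchangeable. On Day 3 they are not: the 87 min sample is the only one near the end of the infusion, where the parent drug peaks. Its neighbours are at 25 min, early in the infusion, and at 4 h, well after it. A profile without it still yields a number for Cmax, tmax and AUC, and nothing in the SAP marks that number as unfit.

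Parent Cmax,ss and AUCτ,ss are named PK endpoints, and the selexipag mixed-model table (PK_MM_SEL, SAP 12.8) is a key deliverable. The ratios are estimated within each dose level, from about 18 evaluable subjects spread over up to eight levels, so one distorted profile can weigh heavily.

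The direction matters too. From the single-dose AUCs in Protocol 1.2.4 and the dose pairs in Protocol Table 1, parent AUC would be higher after i.v. dosing: (11.16/200 × 225) / (11.04/400 × 200) = 12.56/5.52 = 2.3-fold. That projection comes from healthy subjects and a different formulation. A downward error on the i.v. side would hide part of such an excess.

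**Working it through.** **Infusion (Protocol 5.1.4).** Step 1: "Start with an infusion rate of 20 mL/h (0.333 mL/min) for 15 min for the first 5 mL". Step 2: "Increase infusion rate to 37.5 mL/h (0.625 mL/min) for 72 min for infusion of the remaining 45 mL". Check: 20 × 0.25 = 5 mL and 37.5 × 1.2 = 45 mL, total 50 mL; 15 + 72 = 87 min. The plan's figures reproduce, so the 87 min sample is the end-of-infusion sample.

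**Neighbouring samples.** By 25 min, 5 + 37.5 × 10/60 = 11.25 mL has been infused, or 22.5% of the dose. The 4 h sample falls 4 − 1.45 = 2.55 h after the infusion ends.

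**Assumptions.** One compartment for the parent, first-order formation and loss of the metabolite, steady state on 12-hourly dosing. Half-lives are assumed: parent 0.5–7.3 h. The upper end is not arbitrary. Protocol 3.2 says that the i.v. period suffices to regain steady state. If that means 90% within the 24 h before the Day 3 profile, the half-life is at most 24/log2(10) = 7.2 h.

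**Parent formulas** (dose 1, volume 1, k = ln 2/t½; rates 0.1/0.25 = 0.4 per h, then 0.9/1.2 = 0.75 per h):

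- C87 = C0·e^(−1.45k) + (0.4/k)(1 − e^(−0.25k))e^(−1.2k) + (0.75/k)(1 − e^(−1.2k)), with C0 = C87·e^(−10.55k)
- C25 = C0·e^(−0.417k) + (0.4/k)(1 − e^(−0.25k))e^(−0.167k) + (0.75/k)(1 − e^(−0.167k))
- C4h = C87·e^(−2.55k)
- True AUC over the interval = 1/k

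Example, t½ = 1 h: C87 = 0.651, C25 = 0.200, C4h = 0.111. Retained Cmax is 0.200/0.651 = 0.307 of the 87 min value. The six-point trapezoid gives 0.788 against 1/k = 1.443, a ratio of 0.546.

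| Parent t½ (h) | C25/C87 | C4h/C87 | Retained Cmax, from | AUC / true | AUC / seven-sample AUC |
|---|---|---|---|---|---|
| 0.5 | 0.393 | 0.029 | 0.393, 25 min | 0.549 | 0.406 |
| 0.8 | 0.328 | 0.110 | 0.328, 25 min | 0.519 | 0.435 |
| 1 | 0.307 | 0.171 | 0.307, 25 min | 0.546 | 0.480 |
| 1.3 | 0.290 | 0.257 | 0.290, 25 min | 0.600 | 0.549 |
| 1.5 | 0.284 | 0.308 | 0.308, 4 h | 0.634 | 0.591 |
| 2 | 0.283 | 0.413 | 0.413, 4 h | 0.704 | 0.673 |
| 2.5 | 0.295 | 0.493 | 0.493, 4 h | 0.754 | 0.730 |
| 5 | 0.414 | 0.702 | 0.702, 4 h | 0.870 | 0.861 |
| 7.3 | 0.513 | 0.785 | 0.785, 4 h | 0.909 | 0.905 |

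The last two columns differ because the linear rule overshoots the model AUC even with all seven samples when the half-life is short. The Cmax loss falls below 20% only if t½ exceeds 2.55 × ln 2/(−ln 0.8) = 7.9 h.

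**Effect on the i.v./oral ratio.** One affected subject among n multiplies the geometric mean ratio by r^(1/n). For Cmax with r from 0.307 to 0.785, the factor is 0.79 to 0.95 at n = 5 and 0.94 to 0.99 at n = 18. The dip to 0.29 near 1.3 h worsens the lower ends by about one percentage point or less.

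**ACT-333679.** I took parent half-lives of 0.5, 1, 2 and 3 h and metabolite half-lives of 0.5, 1, 2, 4, 6, 8 and 10 h. Retained Cmax equals the scheduled-sample Cmax in 22 of 28 combinations, because the highest scheduled sample is at 4 h or later. The six exceptions (0.19, 0.50, 0.50, 0.90, 0.90, 0.94) all have a metabolite half-life of 2 h or less. AUC is 0.88 or more of true whenever the metabolite half-life is 4 h or longer; at shorter half-lives it can fall much further.

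**The case against.** A reader might infer that i.v. Cmax in general is badly understated and that the exposure comparison behind the primary objective is compromised. The documents do not support that. The exposure objective (Protocol 2.1) names ACT-333679, and the i.v. dose targets its AUC. Under the model, that analyte usually peaks after the infusion ends, so the lost sample does not set its Cmax. The tmax comparison described in the SAP text (7.8.4.3 and 8.2.2.4) is also for ACT-333679; only the output list adds selexipag. Declaring every parameter of both analytes not evaluable would discard mostly sound data on the analyte that matters most. This objection stands, and it limits the point to the parent.

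The trigger is narrow. Day 3 samples must come from the opposite arm (Protocol 7.2.5.1.2). A wrong-arm set-up could well affect both the 25 min and 87 min samples, and two exclusions already remove the subject. This also stands.

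All PK intervals are descriptive, with no equivalence margin, and deviations and individual ratios are listed, so an affected profile could be traced. That limits the consequence, but the summary ratio would still be wrong.

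The existing safeguards do not close the gap. After a code 312 exclusion, the retained 25 min or 4 h value is perfectly plausible, so the implausible-value clause does not apply. Protocol 10.1.5 names availability of measurements as a PKS criterion, but the SAP turns it into a count. Additional rules before lock are optional, and none covers this case.

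**Conclusion.** The gap is real for parent selexipag. Followed literally, the SAP keeps the subject and reports an i.v. Cmax,ss that is about 31–49% of its 87 min value at half-lives of 0.8, 1, 1.5, 2 and 2.5 h (29% near 1.3 h), and still about 78% at 7.3 h. AUCτ,ss is about 52–91% of true. The selexipag i.v./oral ratio is biased downward, most of all in small dose levels.

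The size rests on assumed half-lives and a one-compartment model. The direction does not depend on the exact half-life within the range examined. It is a conditional defect: it takes effect only if the 87 min sample alone is excluded or missing. For ACT-333679 the effect is nil on Cmax in most scenarios and modest on AUC unless its half-life is short, so no general claim about i.v. exposure follows.

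**What to change.** Add to the Table 3 footnote: if the Day 3 87 min sample is excluded or missing, that subject's selexipag i.v. Cmax,ss, tmax,ss and AUCτ,ss are not evaluable and are left out of the selexipag ratio, tmax and power-model analyses. Troughs are kept. ACT-333679 parameters stay in the main analysis, with a sensitivity analysis that omits that subject's ACT-333679 values. SAP 4.1.5 already allows such a rule before database lock.

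The cost is one subject's parent parameters. Treating the comparison as paired with unchanged SD, the 90% CI log half-width is proportional to t(0.95, n − 1)/√n. From 18 to 17 subjects it goes from 1.740/√18 = 0.410 to 1.746/√17 = 0.423, about 3% wider. From 5 to 4 it goes from 2.132/√5 = 0.953 to 2.353/√4 = 1.177, about 23% wider. In a small dose level that is a noticeable loss of precision, accepted in exchange for removing the bias.

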4.2 Usage of the analysis sets

An overview on the usage of the analysis sets for summary tables and listings is given in [Table 4](#).

Table 4 Overview of the different analysis sets and their usage

Analyses/ Data Displays	Screened analysis set	Safety analysis set	i.v. Safety analysis set	Pharmacokinetic analysis set
Demographic data (ICH E3 14.1)				
Subject disposition	✓	(✓)*		
Protocol deviations	✓			
Inclusion/ Exclusion in Analysis Sets	✓			
Subject characteristics (Demographics, disease characteristics, medical history)		✓		
Concomitant therapy		✓		
Study completion		✓		
Study treatment exposure and compliance		✓	✓**	
PK data				
PK endpoints, Period 1 & 2				✓
Safety data (ICH E3 14.3)				
Adverse Events, Clinical Laboratory, ECG, Vital Signs, Body Weight and WHO FC**				
Period 1		✓		
Period 2			✓	
Period 3			✓	
Period 1 & 2		✓		
Period 2 & 3& FU			✓	
Period 1 & 2 & 3 & FU		✓	✓	
Appendices (ICH E3 16.1.7 and 16.2)				
All data collected in the clinical database				
Listings	✓	✓		

* Denominators for disposition will be based on the safety set. ** Tables will be produced for the SAF only if SAF and i.v. SAF are identical. ECG = electrocardiograph; FU = Safety Follow-Up; i.v. SAF = intravenous Safety Analysis Set; PK = pharmacokinetic; SAF = Safety Analysis Set; WHO FC = World Health Organization functional class.

5 STUDY SUBJECTS VARIABLES AND ANALYSES

All summaries described in this section will be displayed separately for the two subject cohorts, i.e., subjects treated with Uptravi 200–1000 µg b.i.d. and 1200–1600 µg b.i.d., as well as for all subjects in the analysis set.

The summary tables, figures and listings will use the analysis sets shown in [Table 4](#).

5.1 Subject disposition

The summaries of subject disposition and screening failures will be prepared on the SCR. Summaries of study completion/discontinuation and study treatment completion/discontinuation will be prepared on the SAF:

5.1.1 Subject disposition and enrollment into analysis periods

Subject disposition will be summarized by presenting the number of subjects screened, enrolled and then number and percentage of subjects entering each analysis period [see [Section 2.3](#)], number and percentage of subjects treated with one, two, and three doses of i.v. selexipag as well as the number and percentage of subjects completing or discontinuing i.v. treatment or the study.

In addition, a summary of disposition by site and country will be prepared.

5.1.2 Screening failures

Screening failures are subjects who were not enrolled into the study, i.e., subjects who did not enter Period 1 of the study.

The number of screening failures will be shown in the disposition table. Reasons for screening failure will be listed.

5.1.3 Study completion/discontinuation

Subjects who received at least one dose of i.v. selexipag and who have completed the follow-up period will be considered study completers.

Subjects may discontinue from the study by withdrawal of consent, loss to follow-up, death, or investigator or sponsor decision. Details of study discontinuation are collected in the electronic case report form (eCRF).

The number and percentages of subjects who completed or prematurely discontinued the study, and reasons for discontinuation from the study will be summarized in a table and in a listing.

5.1.4 Study treatment completion/discontinuation

The number and percentage of subjects who completed or prematurely discontinued i.v. selexipag treatment, and reasons for premature discontinuation from i.v. selexipag treatment as captured in the eCRF will be summarized in a table and in a listing.

5.2 Protocol deviations

The analysis of protocol deviations (PDs) will be prepared on the SCR.

PDs will be based on the PD code list. The PD code list may be updated during the course of the study, but before database closure. The number and percentage of subjects who had an important PD will be summarized overall. All PDs will be summarized overall and by country.

All PDs will be listed. This listing includes all deviation descriptions, identifiers and categories.

5.3 Exclusion from analysis sets

The number and percentage of subjects in each analysis set, as described in Section 4.1, will be summarized in a table together with the number and percentage of subjects excluded from any analysis set, together with the reasons for exclusion. A listing of subject participation in the different analysis sets will be produced.

5.4 Subject characteristics

Subject characteristics will be summarized on the SAF.

5.4.1 Demographics

Baseline demographics, body weight and height will be summarized. The summary will include:

- Age (years)
- Sex (categorized as: Male, Female)
- Race (categorized as: American Indian or Alaska Native, Asian, Black or African American, Native Hawaiian or other Pacific Islander, White, Other)
- Ethnicity (categorized as: Hispanic or Latino, Not Hispanic or Latino, Unknown)
- Body weight (kg)
- Height (cm)
- Country (assigned in the eCRF based on the list of sites).

In addition, the following variables will be derived:

- Age (years) in category, i.e., $>= 18 - < 65$, $>= 65$ years
- Body mass index (kg/m^2)

Demographic characteristics will be summarized using descriptive statistics for continuous and categorical data. Demographic characteristics will also be listed.

For disclosure of results to EudraCT, a summary table will be created showing age (years) in categories 18–64, 65–84, and > = 85.

5.4.2 Baseline disease characteristics

Baseline disease characteristics comprise the specific medical history (time since the initial diagnosis of PAH, and etiology of PAH as well as Uptravi dose) assessed at the screening visit and the WHO functional class (WHO FC) at Day 1.

Baseline disease characteristics will be summarized using descriptive statistics for continuous and categorical data. Time since initial diagnosis of PAH will be summarized in months.

Baseline disease characteristics will be listed.

5.4.3 Other baseline characteristics

The results of a physical examination will be listed.

5.4.4 Medical history

Medical history includes relevant previous and/or concomitant diseases or diagnoses prior to or ongoing at Screening visit, respectively. They are recorded on the ‘Medical History’ eCRF page. Reported terms will be coded using the latest version of the Medical Dictionary for Regulatory Activities (MedDRA) at database lock, Version 21.0.

Previous diseases or diagnoses are medical history events which are not ongoing at screening, i.e., they have an end date prior to or equal to the Screening visit.

Concomitant diseases or diagnoses are all medical history events that are not considered as previous events.

Previous and concomitant diseases/diagnoses will be summarized separately by tabulating the number and percentages of subjects with each disease/diagnosis by system organ class (SOC) and preferred term (PT).

Previous and concomitant medical diseases/diagnoses will be listed.

5.4.5 Previous and concomitant therapies

Previous and concomitant therapies are collected continuously in the eCRF. The reported names will be coded using the WHO drug code dictionary (WHODD) and the anatomic therapeutic chemical (ATC) class code.

Previous therapies are therapies which ended prior to baseline [see Section [10.2](#)].

Ongoing therapies are therapies that were started prior to baseline and are ongoing at study treatment start.

Study concomitant therapies are therapies that were started or dose changed (of those ongoing at baseline) during the respective analysis period [see [Table 2](#)].

Previous therapies, ongoing therapies, and study concomitant therapies will be summarized separately by Level 4 ATC class and PT. The study concomitant therapies summary will be displayed by study period.

The summaries will exclude PAH-specific therapies [see Section [5.4.5.1](#)].

All recorded terms will be reported together in one listing together with flags indicating the type of therapy.

